Name	Created	Modified Date
------	---------	---------------

There are no items to display

ID: VIEW4E02805A7E400
Name: v2_Supporting Literature

Study Procedures

If you uploaded a separate research protocol document in the 'Research Protocol' page, cite the applicable section and page numbers from that document in the answer boxes below. (If this study is a collaborative UM/VA study please list each procedure that is being conducted and the locations where it is being conducted.)

1 * Describe all procedures being performed for research purposes only (these procedures would not be done if individuals were not in the study) and when they are performed, including procedures being performed to monitor subjects for safety or to minimize risks:

The study involves 4 visits to the Maryland Psychiatric Research Center (MPRC). Scheduling of these visits is flexible and depends on the participant's schedule. The only limitation is that the third and fourth visits are scheduled with at least one intervening day, and that no more than three months pass between any consecutive visits.

1. Consent and Screening visit:

After Informed Consent has been obtained, participant will undergo the following screening procedures:

- Verification of age.
- The Standard Clinical Interview for DSM (SCID), to determine the presence/absence of current psychiatric conditions. For some participants, a SCID will have already been obtained and does not have to be repeated.
- Medical history targeted at the cardiovascular, neurological, cognitive and other exclusion criteria.
- Blood pressure and heart-rate reading.
- ECG (12-lead with 3-5 minute rhythm strip).
- Urine drug test, as a possible indication for substance abuse or dependence (may be repeated at any time during the study if intoxication is suspected)
- Alcohol breathalyzer test, as a possible indication for alcohol abuse or dependence (may be repeated at any time during the study if intoxication is suspected)
- Urine pregnancy test for females
- Targeted questions about smoking history in the form of the Nicotine Dependence and the Nicotine Use Questionnaire
- Breath CO reading, as an indicator of smoking status and frequency
- Listing of all currently taken medication
- Vision test
- The Wechsler Abbreviated Scale of Intelligence (WASI), as an indicator for possible mental retardation

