2. Stroop paradigm: In our simplified version, color-words are presented, and subjects say aloud, as quickly as possible, the color in which the word is written. For congruent trials, the color-word is presented in a matching color (e.g. RED in red), for incongruent trials in a non-matching color (e.g. RED in blue). We focus on differences between congruent and incongruent trials, omitting neutral trials to allow for more trials per condition for greater measurement reliability. This task repeatedly revealed increased Stroop interference in schizophrenia (104). Responses are recorded by a microphone connected to a serial response box with voice key and time stamping hardware.

- Participants perform the MATRICS Consensus Cognitive Battery (MCCB) mazes, as a measure of reasoning/problem solving ability.

- Participants perform the Wechsler Test of Adult Reading (WTAR) as a measure of premorbid functioning.

- Nicotine patch toleration: At session end, participants are asked to wear a nicotine patch (21 mg/24 hrs) for at least 4 hrs, to ensure that it is tolerated. The patch is applied to the upper arm, to be easily removable at home. Aside effects checklist is completed just prior to patch application. The research assistant will follow up with the participant by phone, approximately 4 hrs after patch application, to inquire about any potential side effects using the same checklist. The participant is asked to remove the patch and call the research assistant earlier if they experience any side effects that cause them significant discomfort. If any greater-than-mild adverse effects are reported, the dose will be reduced to 14 mg/24 hrs in the Ad Libitum Smoking Session (see below).

3. Nicotine Discrimination Session (~6 hrs):

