After the last discrimination trial, a breath CO reading (x2) is taken, and participants are asked to smoke one research cigarette (A or B) of their choice (not through the CReSS, to create more naturalistic conditions). Choice is recorded. Independent thereof, participants will always be given the VLNC cig. Another CO breathalyzer measurement is taken immediately after smoking to measure the CO-boost from this cigarette, and participants complete the MTWS, AWS, QSU, and mCEQ one last time.

4. Ad Libitum Smoking Session (~8.5 hrs), scheduled ≥ 2 days after the Discrimination Session:

Participants are instructed not to smoke or ingest any nicotine-containing products from waking up until session start at ~9 am, verified by expired CO ≤ 7 ppm. If the CO threshold is exceeded, the session may be rescheduled. Female participants also provide a urine sample for repeat pregnancy testing, which would end participation.

Anicotine patch is then applied (21 mg/24 hrs; if previously not tolerated: 14 mg/24 hrs). Participants deposit their own cigarettes with the research assistant, and a box of VLNCcigs is provided. More VLNCcigs will be dispensed if needed - smoking is ad libitum. Participants are not told that the research cigarettes are virtually nicotine-free, but the consent form states that research cigarettes and patches may differ in nicotine yield from conventional products. For the next 8 hrs, participants stay at the MPRC, settled in a ventilated fire-proofed smoking room with access to the internet and DVDs. In the first hour, breakfast is offered, at noon, lunch is provided, at 3 pm a light snack. The research assistant's desk is adjacent to the smoking room, separated by a semitransparent window; he is available throughout the day. The research assistant records the time of each smoke, and the number of VLNCcigs smoked each time. After 8 hrs, another breath CO breathalyzer reading ($\times 2$) is obtained - the main outcome variable. The secondary outcome, the decline in VLNCcig smoking across the session, is obtained by subtracting the total number of VLNCcigs smoked in the last 2 hrs from that smoked in the first 2 hrs.

2 * Describe all procedures already being performed for diagnostic or treatment purposes (if not applicable to the study, enter "N/A"):

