Some participants may already have done a SCID in the context of clinical care or another study. If this SCID was done at the MPRC, it will not be redone. The diagnostic information will have entered clinical records and will be accessed under a partial HIPAA privacy waiver.

3 * Describe the duration of an individual participant's participation in the study:

The shortest time within which the study can be completed by any participant is 1 week. A maximum of 3 months may expire between any of the four sessions described above (although efforts will be made to not exceed 2 weeks). Thus, the maximum completion time is 9 months.

4 * Describe the amount of time it will take to complete the entire study:

The is a two-year study.

5 * Describe any additional participant requirements:

None.

ID: VIEW4E0280585B400
Name: v2_Study Procedures

Sample Size and Data Analysis

If you uploaded a separate research protocol document in the 'Research Protocol' page, cite the applicable section and page numbers from that document in the answer boxes below.

1 * Provide the rationale and sample size calculations for the proposed target population:

Power analyses indicate that, at $\beta=0.8$, $N=45$ per diagnostic group would enable detection of medium effect sizes (Cohen's $d=0.6$, Cohen's $f=0.3$) with the analyses described below. To prepare for a 20% attrition rate, we will randomize 112 participants for 90 completers. Based on an expected 20% screening failures, we anticipate that screening 140 volunteers will result in 112 enrollments, but to be on the safe side, we set the enrollment ceiling at 160.

2 * Provide the plan for data analysis. Include in the description the types of comparisons that are planned (e.g., comparison of means, comparison of proportions, regressions, analysis of variance, etc.), which is the primary comparison/analysis, and how the analyses proposed will relate to the primary purposes of the study:

- Hypothesis 1 (smoking is under greater cue control in SmoSz than SmoCon) is tested by two-sample t-test comparing groups on breath CO after 8 hrs of ad libitum VLNCcig smoking (ANCOVA if group matching is suboptimal for 1 or more variables). Secondary analysis: ANOVA (or ANCOVA) to compare groups on the number of VLNCcigs smoked in the first vs. last 2 hrs of the Ad Lib Smoking Session (group x time point).

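### No pregnancy test is listed before the first 21 mg nicotine patch at the end of Session 2, so that patch relies on the screening result

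*Combined protocol and SAP*

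**What the plan says.** Being pregnant or lactating is exclusion criterion 9 (Eligibility). Study Procedures, item 1, lists two pregnancy tests.

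- Part 1, the screening visit: "Urine pregnancy test for females".
- Part 4, the Ad Libitum Smoking Session, before the patch goes on: "Female participants also provide a urine sample for repeat pregnancy testing, which would end participation".

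The first study patch falls between these two tests. Under nicotine patch toleration in part 2: "At session end, participants are asked to wear a nicotine patch (21 mg/24 hrs) for at least 4 hrs". It is meant to be taken off away from the clinic: "The patch is applied to the upper arm, to be easily removable at home". Supervision is by telephone: "The research assistant will follow up with the participant by phone, approximately 4 hrs after patch application". A side effects checklist is the only check listed before this patch.

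On timing, item 1 requires that "no more than three months pass between any consecutive visits". Item 3 repeats the limit ("A maximum of 3 months may expire between any of the four sessions described above") and adds an aim that "efforts will be made to not exceed 2 weeks".

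Two other sections mention pregnancy testing. Research Related Risks, under general risk minimization, gives a single repeat before the Laboratory Smoking Session, a title that none of the four listed visits carries. Sample Collection/Analysis, item 4, places urine testing for drugs and pregnancy at screening and when intoxication is suspected. Neither puts a routine test at Session 2.

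**The concern.** The protocol judges a same-day pregnancy test worthwhile before the patch at Session 4. It does not apply that check to the other patch use, which is the same product at the same or a higher dose, and it gives no reason for the difference. The unchecked use is also the less supervised one. At Session 4 participants stay on site for 8 hours and hand over their own cigarettes; at Session 2 outpatients leave with the patch on.

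At stake is a pregnancy that began after screening, or too close to it to be detected. Such a participant no longer meets the entry criteria but would receive study nicotine at Session 2, and again from the research cigarettes at Session 3, before the next listed test. This is a participant-safety matter; no estimate or test in the analysis plan depends on it.

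**Working it through.** **Does the 3-month limit apply to the interval from screening to Session 2?** Four visits make 3 intervals, and 3 × 3 months = 9 months. That reproduces the maximum completion time stated in Study Procedures, item 3, so the limit applies to each interval, including the first.

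**Age of the latest pregnancy test when study nicotine is given.** Add up the intervals since the last listed test.

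| Visit | Target pace, as written | Permitted maximum, as written | Permitted maximum, with a Session 2 test |
|---|---|---|---|
| Session 2 (21 mg patch) | 1 × 2 weeks = 2 weeks | 1 × 3 months = 3 months | same day |
| Session 3 (research cigarettes) | 2 × 2 weeks = 4 weeks | 2 × 3 months = 6 months | 1 × 3 months = 3 months |
| Session 4 (patch) | same day | same day | same day |

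At the fastest pace (all four visits within 7 days, Session 4 at least 2 days after Session 3), Session 2 is no later than 7 − 2 = 5 days after screening.

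**Study nicotine given before the next listed test.** At Session 2 this is one 21 mg/24 h patch for at least 4 hours. At Session 3 the 0.8 mg cigarette is sampled in 2 reference trials and in 2 of every 4 discrimination trials, so 2 + 4 = 6 times, four puffs each.

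**Rough size of the patch exposure.** The documents give neither the release profile nor own-brand yields. Assume uniform release, 0.8 mg per own-brand cigarette, and the minimum of 10 a day.

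- Patch: 21 × 4/24 = 3.5 mg for 4 hours; 21 mg if worn for the full 24 hours.
- Own smoking: 10 × 0.8 = 8 mg per day, so 14 × 8 = 112 mg over 2 weeks and 90 × 8 = 720 mg over 3 months.
- Patch relative to own smoking over a 2-week gap: 3.5/112 = 3% to 21/112 = 19%.
- Over a 3-month gap: 3.5/720 = 0.5% to 21/720 = 2.9%.

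A pregnancy would cover only part of either gap, so these percentages show order of magnitude only.

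**Number of extra tests.** Sample Size and Data Analysis, item 1, expects 140 screened and 20% screen failures: 140 × 0.8 = 112 going on. The sex split is not given. If all were female, that is 112 dips. At the enrollment ceiling of 160 with the same failure rate it is 160 × 0.8 = 128. The figure cannot exceed 160.

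**The case against.** The strongest reply is proportionality. Everyone enrolled already smokes at least 10 a day, the required wear is 4 hours, and on the rough figures above that is less than half a day's own smoking (3.5 mg against 8 mg). Visits are meant to be no more than 2 weeks apart, so 3 months is a limit and not the expected gap. Testing at entry and before the longest smoking session is a reasonable choice, and nothing in the protocol contradicts it. All of this stands, and it keeps the point small. It does not remove it: the argument that participants already smoke applies equally at Session 4, where the protocol still tests.

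It may also be said that Session 3 is more exposed than Session 2, since its latest test can be 6 months old. That is true. A Session 2 test halves that maximum but does not make it same-day.

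Not every participant leaves the site with the patch, because inpatients from the Treatment Research Program are also recruited. The consent form, patch insert and Study Manual are not available here and may contain instructions on suspected pregnancy.

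A reader might infer from Research Related Risks, part a, item 2, that the patch delivers more nicotine than these participants usually take in. The documents do not support that for this use. The sentence explains when nausea can occur, gives no wear time, and says nothing about a 4-hour wear.

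**Conclusion.** The gap is real and of low importance. As written, the Session 2 patch relies on a pregnancy test about 2 weeks old at the target pace and up to 3 months old at the limit; at Session 3 the latest test can be up to 6 months old. These ages follow directly from the visit rules. The statement that no test precedes the Session 2 patch rests on the listed procedures and on the two other sections that mention pregnancy testing.

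Few cases are likely, although the documents give no pregnancy rate from which to estimate a number. The added exposure is small on the stated assumptions. It would go too far to read this as a protocol that neglects pregnancy or is unsafe: it tests at entry, repeats the test once, and ends participation on a positive result. Sample size, power and the planned analyses are unaffected.

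**What to change.** In Study Procedures, item 1, part 2, add a urine pregnancy test for female participants before the patch is applied, with a positive result ending participation as at Session 4. Bring the pregnancy-testing statements in Research Related Risks and Sample Collection/Analysis into line.

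The cost is a small amendment plus one dip and a few minutes per female participant, using a test already run at two visits. The number of dips is at most about 112 as planned, about 128 at the enrollment ceiling with 20% screen failures, and never more than 160.

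A participant found pregnant at Session 2 leaves before Session 3, so her discrimination data are lost. If still pregnant at Session 4 she would be withdrawn there in any case, before the primary breath CO reading, so no primary outcome is given up.

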A factor which may facilitate such stimulus-controlled smoking routines in PSZ is that smokers with schizophrenia (SmoSz) appear remarkably insensitive to subjective effects of nicotine. According to theories of drug dependence, drug effects insensitivity would facilitate a habitual, cue-locked drug taking mode.

Furthermore, automatized drug-taking is reportedly associated with frontoexecutive control deficits, a hallmark of the neurocognitive profile of schizophrenia. Thus, nicotine insensitivity and cognitive control deficits may facilitate automatized, stimulus-driven smoking in SmoSz.

The overall aim of this proposal is to determine whether tobacco smoking in PSZ is under disproportionately strong cue control, and to test whether insensitivity to the subjective effects of nicotine and/or cognitive control deficits can account for this.

Aim 1 is to test whether tobacco smoking behavior is under greater cue control in SmoSz than in matched healthy control smokers (SmoCon). Approach: Indices of cue-controlled smoking are obtained by quantifying the degree to which virtually nicotine-free cigarettes can maintain smoking behavior over eight hours under standardized laboratory conditions, in the presence of transdermal nicotine replacement. Nicotine-free cigarettes evoke a near-complete set of internal and external stimuli and behavioral routines associated with tobacco smoking, but without ensuing nicotine delivery, thus capturing the essence of stimulus control over smoking behavior.

Aim 2 is to test whether SmoSz are less sensitive to the subjective effects of nicotine than SmoCon. Approach: In a standardized laboratory paradigm, SmoSz and SmoCon discriminate research cigarettes of differing nicotine yields, and report on subjective state measures after each cigarette.

Aim 3 is to determine whether nicotine insensitivity is related to cue-control over smoking behavior, and can account for the group difference therein.

Aim 4 is to determine whether cognitive control deficits are related to cue-control over smoking behavior, and can account for the group difference therein. Approach: A cognitive control index will be derived from tasks selected from the RDoC matrix.

2 * Discuss the research design including but not limited to such issues as: probability of group assignment, potential for subject to be randomized to placebo group, use of control subjects, etc.:

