Maryland Psychiatric Research Center

www.mprc.umaryland.edu"

Text added to VAflyers only:

"This research is not VA research, will not be conducted by VA, has not been reviewed by VA's Institutional Review Board, and is not endorsed by VA. VA is not responsible for any costs incurred by a Veteran if the Veteran enters the study as a research subject. The announcement is being provided for information only."

1.3 * Upload advertisement(s) here:

Name	Created	Modified Date
Flyer with tear-offs with transportation(0.05)	3/10/2022 11:39 AM	9/23/2022 11:19 AM
Flyer with tear-offs(0.05)	6/20/2019 9:47 AM	9/23/2022 11:11 AM
Flyer without tear-offs with transportation(0.03)	3/10/2022 11:40 AM	9/23/2022 11:04 AM
Flyer without tear-offs(0.04)	7/14/2021 10:14 AM	9/23/2022 11:04 AM
Coaster(0.02)	6/16/2022 4:39 PM	9/23/2022 11:03 AM
Flyer without tear-off facebook(0.04)	9/6/2022 9:44 AM	9/23/2022 11:03 AM
Flyer with tear-offs VA(0.01)	1/12/2022 11:46 AM	1/12/2022 11:46 AM
Flyer without tear-offs VA(0.01)	1/12/2022 11:46 AM	1/12/2022 11:46 AM

Research Related Risks

If you uploaded a separate research protocol document in the 'Research Protocol' page, cite the applicable section and page numbers from that document in the answer box below.

1 * Individually list each research-related risk, using a separate line for each. Next to each risk, delineate the likelihood/seriousness of the risk, and the provisions for minimizing the risk:

Risks associated with this study include those related to: a) nicotine patch administration, b) smoking research cigarettes, c) nicotine withdrawal, d) completing questionnaires, and e) loss of confidentiality. All expected adverse events are non-serious.

a) Risks related to nicotine patch administration:

1. Skin irritation is one of the most common side effect of nicotine patches but is expected to be of minor severity and to dissipate spontaneously after patch removal.
2. Nausea can occur in smokers if more nicotine is ingested from the patch than is usually ingested via smoking, which may be the case for some participants. Nausea is expected to dissipate spontaneously within 2 h after patch removal.
3. Vomiting is expected to be rare; the patch will be removed if nausea occurs, which is likely to prevent most occurrences of vomiting.
4. Palpitations and diaphoresis may occur but are not expected to cause severe discomfort.
5. Headache: This is a minor risk.

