6. Abdominal pain and dry mouth are expected to be rare, but may cause significant discomfort.
7. Restlessness, sleepiness, dizziness or temporary mood changes may occur but are expected to be mild.

Risk Minimization for all of the above risks: Participants are informed of this risk in the consent form and are aware that they can end participation and remove or ask for the patch to be removed if any side effect becomes too unpleasant. Participants will wear the 21 mg/24 h patch prior to the Ad Libitum Smoking session, and if any side effects occur, they will receive a 14 mg/24 h patch in the Ad Libitum Smoking session.

b) Possible adverse events related to smoking research cigarettes:

The nicotine yield of either the research cigarettes (0.03 and 0.8 mg) is no higher than that of most commercially available cigarettes. Tar yield is comparable. Risks associated with smoking the research cigarettes are comparable to smoking own-brand cigarettes. However, because the research cigarettes to be used in the Ad Libitum Smoking Session are free and of low nicotine yield, participants may smoke more in the Ad Libitum Smoking Session than they would usually have done. As a result, they may be exposed to more of the harmful components of tobacco smoke (other than nicotine) on this day.

c) Signs and symptoms of nicotine withdrawal may include irritability, difficulty concentrating, anxiety, increased appetite, depressed mood, restlessness, craving, and insomnia (the latter is not expected in this study due to the short duration of withdrawal). Given that participants are only nicotine deprived from waking up in the morning until approximately 11 am (at which time they will have obtained nicotine from the sampled research cigarettes in the Cigarette Discrimination Session or absorbed nicotine from the patch in the Ad Libitum Smoking Session), all of these symptoms are expected to be mild, if present.

Risk Minimization: Nicotine patch is administered in the Ad Libitum Smoking Session in which only very low nicotine content cigarettes are smoked. Both the Cigarette Discrimination Session and the Ad Libitum Smoking Session are scheduled to begin at 9 am, to minimize the period between waking up and nicotine ingestion.

d) Participants may be bored by being asked to answer the same questions repeatedly, find the procedure tiring, or perceive the questions as intrusive.

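### Two conflicting triggers for the 14 mg/24 h patch leave the dose undefined, in the primary-outcome session, for participants with only mild side effects

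*Combined protocol and SAP*

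**What the plan says.** All references are to the combined protocol and SAP.

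- **Study Procedures, item 1, part 2 (patch toleration).** Participants wear a 21 mg/24 h patch for at least 4 hours after the cognitive test session. A side effects checklist is completed just before application. The research assistant telephones at about 4 hours "to inquire about any potential side effects using the same checklist". The rule is then: "If any greater-than-mild adverse effects are reported, the dose will be reduced to 14 mg/24 hrs in the Ad Libitum Smoking Session".
- **Study Procedures, item 1, part 4 (Ad Libitum Smoking Session).** The patch is 21 mg/24 h by default, with the exception "if previously not tolerated: 14 mg/24 hrs". No severity grade is attached to the exception.
- **Research Related Risks, item 1(a), risk minimization.** After describing the same 21 mg/24 h trial wear, the text says "if any side effects occur, they will receive a 14 mg/24 h patch in the Ad Libitum Smoking session".
- **Research Related Risks, item 1(a), expected effects.** "Skin irritation is one of the most common side effect of nicotine patches but is expected to be of minor severity", and "Restlessness, sleepiness, dizziness or temporary mood changes may occur but are expected to be mild".
- **Research with Drugs or Biologics, item 1.** Both patch strengths are listed, without a trigger.

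**The concern.** The two triggers govern one decision and use different thresholds. A participant who reports only mild effects satisfies one and not the other, so staff cannot comply with both statements.

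The dose matters because the patch is part of the measurement. Aim 1 quantifies smoking of virtually nicotine-free cigarettes "over eight hours under standardized laboratory conditions, in the presence of transdermal nicotine replacement". Hypothesis 1 is tested by "comparing groups on breath CO after 8 hrs of ad libitum VLNCcig smoking". Neither the t-test nor the fallback ANCOVA (planned for suboptimal group matching) names patch dose. If the rule is read differently from one participant to the next, the dose worn depends on that reading, and a reader of the results cannot tell which rule produced them.

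The risk section is also the protocol's statement of how patch side effects will be limited, and it does not match the operating procedure.

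**Working it through.** **1. Are the statements about the same thing?** Both concern the trial wear of the 21 mg/24 h patch, both set the dose for the Ad Libitum Smoking Session, and both are current text. One says adverse effects and the other side effects, but the documents define no difference, and Study Procedures part 2 uses both terms for this check.

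**2. Apply each rule to each type of participant.**

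| Worst effect on the test patch | Study Procedures, parts 2 and 4 | Research Related Risks, 1(a) | Agree? |
|---|---|---|---|
| None | 21 mg/24 h | 21 mg/24 h (by implication) | Yes |
| Mild only | 21 mg/24 h (by implication) | 14 mg/24 h | **No** |
| Greater than mild | 14 mg/24 h | 14 mg/24 h | Yes |

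Study Procedures does not say outright that mild effects leave the dose at 21 mg/24 h. That follows from the greater-than-mild condition together with the 21 mg/24 h default in part 4.

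**3. Is the disputed row foreseen?** Yes. The risk section ranks skin irritation of minor severity among the most common effects and anticipates several others at mild grade. The 4-hour call asks about any effect, so mild ones can be expected to surface.

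**4. Does anything else settle it?**

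- The exception in part 4 has no grade of its own.
- The drug listing has no trigger.
- Withdrawal of Participants, item 1, deals with adverse effects of the 14 mg/24 h patch, a later step.
- The Study Manual mentioned in the resources section (item 4) is not in the documents, and it could not make two protocol statements agree.

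**5. Size.**

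- Dose gap: 21 − 14 = 7 mg/24 h; 7 / 21 = 0.333.
- Planned completers (Sample Size and Data Analysis, item 1): 2 × 45 = 90.
- Completers with an undefined dose = p × 90, where p is the mild-only share. The documents do not give p. As an assumed range:

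| Assumed p | Completers affected |
|---|---|
| 10% | 0.10 × 90 = 9 |
| 30% | 0.30 × 90 = 27 |
| 50% | 0.50 × 90 = 45 |

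**6. What cannot be computed.** The documents give neither p nor the difference in 8-hour breath CO between the two patch strengths, so no bias or power loss can be derived. The stated sample size does not depend on this point.

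**The case against.** The best counter-argument is that the operating text is coherent by itself. Part 2 points forward to the Ad Libitum session and says the test patch is worn to check that it is tolerated. Part 4 uses the same term, so it can be read as borrowing the graded threshold from part 2. On that reading the conflict is between the procedures and a single sentence in a risk summary. This is fair and narrows the conflict. It does not remove it: the documents state no order of precedence, and the risk sentence is an unqualified commitment about what participants will receive.

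Other points also carry weight:

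- **Frequency is unknown.** Being among the most common effects is a ranking, not a rate. The checklist completed before application also means that symptoms already present need not count as patch effects.
- **Two doses are allowed under either rule.** Reconciling the text will not make the dose uniform. Neither trigger mentions diagnosis, so nothing in the wording favours one group.
- **The effect may be small.** The background section (Justification, item 3) says that substituting nicotine reduces smoking only slightly.
- **Some material was not available.** The checklist itself and the consent pages might show how mild effects are graded.

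These points limit what can be said about consequences. None of them makes the two statements compatible.

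**Conclusion.** The contradiction is real and should be fixed. For participants whose test-patch effects are all mild, the protocol assigns both 21 and 14 mg/24 h in the session that yields the main outcome. The difference is one third of the higher dose. The number affected is unknown, at 9 of 90 completers for each 10 percentage points of mild-only share.

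The conclusion rests on two readings: that adverse effects and side effects mean the same in this check, and that the greater-than-mild condition leaves mild-only participants on the default dose. It does not depend on any assumption about how patch strength affects breath CO. No claim is made that the group difference is biased, that power is reduced or that the sample size is wrong. Which trigger is clinically appropriate is not judged here.

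**What to change.** - **Reconcile the rule.** The investigator and study physician should choose one trigger and state it in identical words in Study Procedures item 1, parts 2 and 4, and in Research Related Risks item 1(a).
- **Check the neighbouring text.** Withdrawal of Participants, item 1, contradicts nothing by itself, but its ungraded reference to adverse effects of the 14 mg/24 h patch should be read against the chosen trigger.
- **Report the dose worn.** Tabulate the number on each patch strength by diagnostic group in the Ad Libitum session. A sensitivity analysis by dose is optional and must not replace the primary Hypothesis 1 test.

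The cost is a short wording amendment, a staff re-briefing and one descriptive table row, with no new visits, assessments or participants. The limitation is that participants already tested keep the dose they wore. The amendment cannot make past sessions uniform, but the table would show what was worn.
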